9.1	CONFIDENTIALITY	20
9.2	CASE REPORT FORMS	20
9.3	RECORD RETENTION	20
10	CLINICAL SITE MONITORING.....	20
10.1	ON-SITE MONITORING	20
10.2	AUDITING AND INSPECTING	20
11	ETHICAL CONSIDERATIONS.....	20
12	STUDY FINANCES.....	20
12.1	FUNDING SOURCE.....	20
12.2	CONFLICT OF INTEREST	20
13	REFERENCES.....	21

List of Abbreviations

AE:	Adverse Event/Adverse Experience
AUC:	Area under the curve
CIS:	Center of Innovation Surgery
CT:	Computed tomography
CTSA:	Clinical and Translational Science Institute
CCRC:	Clinical Cancer Review Committee CFR:
	Code of Federal Regulations
CMS:	Centers for Medicare and Medicaid Services
CRF:	Case Report Forms
CPHS:	Committee for the Protection of Human Subjects
DCC:	Data Coordinating Center
DCE:	Dynamic contrast-enhanced
DCE-MRI:	Dynamic contrast-enhanced magnetic resonance imaging
DHMC:	Dartmouth Hitchcock Medical Center
DSMC:	Data and safety monitoring committee
FDA:	Food and Drug Administration
FI	Fluorescence imaging
GCP:	Good Clinical Practice
Gd-DTPA:	gadolinium-diethylenetriamine penta-acetic acid
GFR:	Glomerular filtration rate
HVHC:	High Value Health Care
ICG:	Indocyanine green
HIPAA:	Health Insurance Portability and Accountability Act
IACUC:	Animal Care and Use Committee
ICF:	Informed Consent Form
iFI:	Intraoperative Fluorescence Imaging
IRB:	Institutional Review Board
I_{max} :	Maximum ICG fluorescence intensity
$I_{max-post}$:	ICG fluorescence intensity at post-debridement
ISM:	Independent Safety Monitor
LAR:	A legally authorized representative
MRI:	Magnetic resonance imaging
NIASM:	National Institute of Arthritis and Musculoskeletal and Skin Diseases
NIH:	National Institutes of Health
NIST:	National Institute of Standards and Technology
NCCC:	Norris Cotton Cancer Center
NSF:	nephrogenic sclerosing fibrosis
OCTOM:	Office of Clinical Trials Operations and Management, NIDCR, NIH
OHRP:	Office for Human Research Protections
OHSR:	Office of Human Subjects Research
OTA:	Orthopaedic Trauma Association
PI:	Principle investigator
PROs:	Patient reported outcomes
QA:	Quality assurance
QC:	Quality Control
RCTs:	Randomized controlled trials
REB:	Research Ethics Board
ROC:	Receiver operating characteristic
SAE:	Serious Adverse Event/Serious Adverse Experience
SOP:	Standard Operating Procedure
SSI :	Surgical site infection

Study Summary

Title	Fluorescence imaging to Guide Debridement of Fracture and Infection
Short Title	ICG fluorescence imaging in trauma patients
Protocol Number	N/A
Phase	Phase I
Methodology	
This will be a prospective observational trial to better understand the range and variation associated with bone/soft tissue perfusion in fracture patients and examine the relationship between perfusion, measured using quantitative Indocyanine green (ICG) fluorescence and complications such as surgical site infection (SSI), persistent SSI, and fracture nonunion. Primary outcome measure is complication (either infection, recurrent infection or nonunion).
 
Eligible consenting patients will receive standard of care treatment for their fracture or infection including irrigation and debridement of their operative site and/or fracture fixation. Participation in this study has no specific benefit to the subject. This treatment is not expected to alleviate the need for surgical intervention. After exposure, 0.1 mg/Kg ICG will be injected intravenously and video rate ICG fluorescence images will be acquired 20 seconds before and 4 minutes after the injection, each before and after debridement. A subset of 38 post-fracture complication patients will undergo surgical treatment for their infection in Center of Innovation Surgery (CIS) and have either an intraoperative DCE-MRI after exposure but before the ICG injection or a preoperative DCE-MRI. Patients receiving surgery in the CIS will be required to sign an additional CIS-specific consent document, Informed consent with MRI.
 
The need for repeat surgical procedure will be left up to the treating surgeon. If repeat procedure is needed, pre- and post-debridement quantitative ICG fluorescence images will be obtained at each procedure.
 
Study participants will be followed at 2 weeks, 6 weeks, 3 months and 6 months from their index study surgery. Complication including index infection, recurrent infection or delaying union/nonunion will be identified at the time of diagnosis and/or during each participant's assessment that occurs during routine outpatient clinic visit. Detailed information on the infection including date of diagnosis, participant signs and symptoms, culture test results, method of treatment(s), and date of resolution will be documented.

Study Duration	Five years
Study Center(s)	Single-center, Dartmouth-Hitchcock Medical Center
Objectives	The primary study objectives are to (1) establish the range and variation associated with bone/soft tissue perfusion in fracture patients and (2) examine the relationship between perfusion, measured using quantitative ICG fluorescence and complications such as SSI, persistent SSI, and fracture nonunion.
Number of Subjects	(1) 176 patients with open fracture patients; (2) 82 patients with a complications (infection or nonunion) following surgical treatment of fracture; (3) 100 patients with closed fracture.

Diagnosis and Main Inclusion Criteria	
Open Fracture Cohort (Cohort 1)
 
 a. Patients 18 years of age or older. b. Open extremity fracture. c. Planned definitive fracture management with external fixation, internal fixation, or joint fusion. d. Will have all planned fracture care surgeries performed by a participating surgeon or delegate. e. Provision of informed consent. 
Complication Cohort (Cohort 2)
 
 f. Patients 18 years of age or older. g. Extremity fracture. h. Prior definitive fracture management with external fixation, internal fixation, or joint fusion. i. Superficial, deep, or organ space SSI (as per CDC criteria) at the fracture site that requires operative management. j. Will have all fracture care surgeries performed by a participating surgeon or delegate. k. Provision of informed consent. 
Closed Fracture Cohort (Cohort 3)
 
 l. Patients 18 years of age or older m. Closed extremity fracture n. Planned definitive fracture management with external fixation, internal fixation, or joint fusion. p. Provision of informed consent.
Study Product, Dose, Route, Regimen	
This protocol is an imaging study which does not specify any change in treatment protocol or and will not alter the surgical course for the patient enrolled, therefore should not be considered an experimental treatment..
 
ICG is an FDA approved fluorescence probe. After skin exposure, 0.1 mg/Kg ICG will be injected intravenously, each before and after debridement. Video rate ICG fluorescence images will be acquired 20 seconds before and 4 minutes after ICG injection, by an FDA approved fluorescence imaging system, (Spy Elite (Novadaq/Stryker US). The imaging is non-contact and the imaging head is at least 50 cm away from the bone.

Duration of administration	Patients are enrolled in the study from time of consent prior to surgery to the end of six months of the follow up period.
Reference methods	N/A
Statistical Considerations	Descriptive statistics will be present (mean and standard deviation) with 95% confidence intervals. We are planning to collect ICG data before and after the debridement. Pearson correlation between ICG parameters (pre-debridement, or/and post-debridement, or/and changes between pre- and post-debridement) and index infection/recurrent will be calculated for each of three patient cohorts. We will also include the corresponding coefficient of determination indicating how much variation in index infection/recurrent can be explained in ICG parameters. Finally, we will evaluate the significance of the correlation coefficient using two sided t-test. P-value less than 0.05 will indicate that the correlation is significant. Then, we will form receiver operating characteristic (ROC) curves to illustrate graphically the performance and to obtain the threshold for differentiating the recurrent infection from non-infection group, of each chosen model. Area under the ROC curve will be used to determine the optimal property for differentiating the recurrent infection patients from the non-infection patients.

1 Introduction

This document is a clinical research protocol and describes a human research study. This study will be conducted according to US and international standards of Good Clinical Practice (FDA Title 21 part 312 and International Conference on Harmonization guidelines), applicable government regulations and Institutional research policies and procedures. All personnel involved in the conduct of this study have completed human subject protection training and primary oncologic surgeons performing study procedures will be trained on this protocol

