7.2 Data and Statistical Analysis

Patient cohort 1:

For the primary outcome, SSI is the dependent variable and bone and tissue perfusion, as measured by ICG fluorescence, is the independent variable. Unplanned fracture-related reoperation is the secondary dependent variable and bone and tissue perfusion as measured by ICG fluorescence, is the independent variable. Descriptive statistics, including means and standard deviations, will be presented with 95% confidence intervals. To select the most important ICG fluorescence kinetic curve-related variables, we will perform a bivariate analysis evaluating whether each variable predicts infection and we will select the variable with the highest individual area under the receiver operating curve (AUC ROC).

Our primary null hypothesis is that the post-debridement maximum ICG intensity ($I_{max-post}$) among patients with SSI is equal to or greater than that in the non-SSI patient group. The primary alternative hypothesis is that $I_{max-post}$ in the SSI group is smaller than that in the non-SSI group. We will then perform Students t-tests and chi-square analyses (depending on continuous or categorical variable status) to determine unadjusted associations between the most important ICG fluorescence variable and SSI. A p-value of 0.05 or less will be considered significant for differences between SSI and non-SSI groups. We will then apply multiple logistic model including ICG fluorescence and previously identified predictors for SSI³⁷⁻³⁹. Wald test will be used to determine if ICG fluorescence or any other predictors are significant in the model. We set the type I error at 5%. Table 7.1 shows a summary of the study outcomes, corresponding

hypotheses, and method of analysis to be performed. We anticipate that we will demonstrate a statistically significant difference between the maximum post-debridement ICG fluorescence in patients with and without SSI

Table 7.1 Summary of Outcome Analysis Plan for patient cohort 1

Objective	Outcome		Hypothesis	Method of analysis
	Name	Type		
Determine the association between post-debridement bone perfusion as measured by quantitative ICG fluorescence and surgical site infection (SSI) in patients with open fracture	SSI	Binary	Mean perfusion will be lower among patients who develop SSI	Students t-test Multivariable logistic regression

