Table 7.2: Summary of Outcome Analysis Plan of patient cohort 2.

Objective	Outcome		Hypothesis	Method of analysis
	Name	Type		
Determine the association between post-debridement bone perfusion as measured by quantitative ICG fluorescence and persistent SSI/treatment failure in patients with SSI	Persistent SSI/Treatment failure	Binary	Mean perfusion will be lower among fracture patients with persistent SSI/treatment failure	Students t-test Logistic regression

Patient cohort 3: Classification into cohort categories (closed fracture, open fracture, complication) is the independent variable and ICG fluorescence magnitude is the dependent variable. Descriptive statistics, including means and standard deviations, will be presented with 95% confidence intervals.

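### The Study Summary and Section 7.2 set different families of significance tests for perfusion and infection, and neither fixes the single test that decides the question in each cohort

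*Combined protocol and SAP*

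**What the plan says.** **Study Summary, Statistical Considerations.** The text reads "Pearson correlation between ICG parameters (pre-debridement, or/and post-debridement, or/and changes between pre- and post-debridement) and index infection/recurrent will be calculated", and the sentence goes on to apply this to each of the three cohorts. For the test itself, "we will evaluate the significance of the correlation coefficient using two sided t-test", and "P-value less than 0.05 will indicate that the correlation is significant". No measure is marked as primary, no adjustment is given, and no correlation is called exploratory.

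**Section 7.2, cohorts 1 and 2.** Each cohort has one stated primary hypothesis: "Our primary null hypothesis is that the post-debridement maximum ICG intensity" (I_max-post) is equal or greater in the SSI group (cohort 1) or the treatment-failure group (cohort 2). The alternative is that it is smaller. Tables 7.1 and 7.2 also give post-debridement perfusion as the objective. The same section, however, first ranks the kinetic-curve variables by AUC. It then uses the t-test, in cohort 1, to "determine unadjusted associations between the most important ICG fluorescence variable and SSI"; cohort 2 is worded in the same way. I_max-post is not named as the variable that enters the test.

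**Section 7.2, cohort 3.** "Classification into cohort categories (closed fracture, open fracture, complication) is the independent variable and ICG fluorescence magnitude is the dependent variable". The analysis is descriptive and infection is not an outcome in it, although Section 3.2 makes SSI the primary endpoint of this cohort.

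Neither section says which of the two plans governs, and the documents contain no multiplicity rule.

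**The concern.** Both sections address the same question, whether perfusion is related to infection, but a reader would run different analyses from each:

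| | Study Summary | Section 7.2 |
|---|---|---|
| Measures | pre, post and/or change | I_max-post in the hypothesis; highest-AUC variable in the test |
| Cohorts tested against infection | 1, 2 and 3 | 1 and 2 |
| Direction | two-sided | directional hypothesis |
| Status | every p<0.05 is significant | one primary hypothesis per cohort |

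The three measures can disagree, and only the post-debridement one matches the objectives in Tables 7.1 and 7.2. Under the Study Summary's rule, a chance result on pre-debridement intensity or on change is called significant on the same terms as a result on I_max-post. The or/and wording also leaves the choice of measure open until the data are seen. The 5% type I error in Sections 7.1 and 7.2 then does not describe the set of results that may be called significant.

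**Working it through.** **1. The plan's own figures.** The documents state no family-wise error rate, so the power figures in Section 7.1 are the ones to reproduce. The inputs are a difference of 24 a.u., SDs of 30 (infected or failed) and 15 (not), and a 5% type I error.

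- Cohort 1, 16 v 144: SE = √(30²/16 + 15²/144) = √57.81 = 7.60, and 24/7.60 = 3.16. The two-sided Welch t-test has power 84.1% (stated 86%).
- Cohort 2, 22 v 52: SE = √(30²/22 + 15²/52) = √45.24 = 6.73, and 24/6.73 = 3.57. The two-sided Welch t-test has power 92.9% (stated 93%).

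One-sided 5% tests would give 91.5% and 96.6%. The stated powers are therefore close to two-sided tests, although the hypotheses in Section 7.2 are directional.

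**2. Number of tests.** For one kinetic parameter the Study Summary allows up to 3 measures × 3 cohorts = 9 tests.

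**3. Reference values for one named test per cohort.** The cohorts are independent, so the chance of at least one false positive is 1 − 0.95^k:

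- one cohort: 5%
- cohorts 1 and 2: 1 − 0.95² = 9.75%
- three cohorts: 1 − 0.95³ = 14.3%

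Nine fully independent tests would give 1 − 0.95⁹ = 37.0%. That is too high here, because change is post minus pre.

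**4. Allowing for that dependence.** Pre and post values were simulated as bivariate normal with no association with infection. Change was post minus pre, and each of the three was tested two-sided at 5%. With p as the chance of any false positive in one cohort, two cohorts give 1 − (1 − p)² and three give 1 − (1 − p)³. The documents give neither the pre/post correlation nor the ratio of the SDs, so both were varied:

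| SD ratio | Pre/post correlation | One cohort | Cohorts 1 and 2 | All three |
|---|---|---|---|---|
| 1 | 0 | 11.5% | 21.7% | 30.7% |
| 1 | 0.5 | 12.2% | 22.9% | 32.3% |
| 1 | 0.8 | 11.8% | 22.3% | 31.5% |
| 1 | 0.95 | 10.9% | 20.6% | 29.3% |
| 2 | 0 | 11.2% | 21.1% | 30.0% |
| 2 | 0.5 | 11.3% | 21.3% | 30.2% |
| 2 | 0.8 | 9.9% | 18.8% | 26.8% |

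Worked example, first row: 1 − (1 − 0.115)³ = 30.7%.

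**5. Check at the planned sizes.** The Pearson t-test was simulated with a binary outcome, equal SDs, 16/160 and 22/74 events, and an assumed 5/90 for cohort 3. At correlations 0, 0.5 and 0.8 it gave 30.5%, 32.4% and 31.9% across the three cohorts. With an assumed 5/100 for cohort 3, and correlations 0.2, 0.5 and 0.8, it gave 31.7%, 33.1% and 31.8%.

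The ranges are therefore about 10-12%, 19-23% and 27-33%, against 5%, 9.75% and 14.3%.

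**The case against.** The strongest reply is that the study does have a deciding test. Section 7.2 states a primary hypothesis on I_max-post for cohorts 1 and 2, and Section 7.1 sizes both cohorts on maximum intensity. On this view the Study Summary is only a loose summary. That stands in part. A reader might infer from the Study Summary that the plan contains no primary hypothesis at all, and the documents do not support that: the gap is in the Study Summary alone. The reply does not settle the matter, because Section 7.2 runs its t-test on whichever variable has the highest AUC in the same data, and no text gives one section precedence.

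A second reply is that nothing says one hit among nine makes the study positive. This is correct. The rule is applied to one correlation at a time, and the cohorts are different populations with their own endpoints in Section 3.2. Pooling them into one error family is a reader's choice, which is why the per-cohort figure is given first.

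Third, or/and may mean fewer than nine tests, and Section 5.2 lets the investigator obtain only one imaging series, so some patients will have no change value. Both points stand as limits on the arithmetic. Fewer tests would help only if the measure were fixed before the data are seen, and it is not. In the other direction, more than one kinetic parameter would raise the count above nine.

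Last, the study is Phase I and observational, it is sized as a pilot (Section 7.1), and no treatment decision depends on it (Section 1.5.2). That lowers the weight of the point. It does not remove it, because Section 7.2 sets a 5% error and anticipates statistically significant differences.

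**Conclusion.** The point holds as an inconsistency between the Study Summary and Section 7.2, with a moderate and conditional effect on error rates. If all three measures are tested for one kinetic parameter and no association exists, the error within a cohort roughly doubles, from 5% to about 10-12%. Across cohorts 1 and 2 it rises from 9.75% to about 19-23%, and across all three from 14.3% to about 27-33%. These figures assume normal data, complete pre/post pairs, correlations from 0 to 0.95, SDs that are equal or differ by a factor of two, and an assumed event count in cohort 3.

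A reader might set the figure of about one third beside the stated 5% and call it a six-fold inflation. The documents do not support that comparison. The 5% applies to one test, whereas the larger figure pools three cohorts and needs all nine tests to be run. The like-for-like comparator for three cohorts is 14.3%.

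The plan should be amended, but in this setting the point does not put the study as a whole in doubt.

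**What to change.** Amend both sections, because a change to the Study Summary alone would leave the AUC-selected test in place and would not secure 5% per cohort.

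- In the Study Summary and Section 7.2, name I_max-post against the cohort's primary endpoint as the single confirmatory test in each of cohorts 1 and 2.
- State one sidedness for that test in both places. Two-sided 5% is the version close to the power figures in Section 7.1; if one-sided is chosen, restate the power.
- Say in Section 7.2 that this test is run on I_max-post and not on the variable with the highest AUC. The AUC ranking can stay as an exploratory analysis.
- Remove the p<0.05 rule for pre-debridement ICG, change in ICG, other kinetic parameters and all cohort 3 infection correlations. Report these as exploratory estimates with 95% confidence intervals.

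This gives 5% per cohort and 9.75% across cohorts 1 and 2. It needs no extra patients or data. The price is that a nominal p<0.05 on one of the exploratory measures can no longer be reported as a confirmed finding.

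### The synopsis's Pearson r, R-squared and t-test of r suit neither a yes/no infection outcome nor the unequal SDs that section 7.1 assumes

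*Combined protocol and SAP*

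**What the plan says.** The Statistical Considerations entry of the Study Summary plans Pearson correlations between ICG parameters (pre-debridement, post-debridement or change) and infection. These "will be calculated for each of three patient cohorts". It adds the "coefficient of determination indicating how much variation in index infection/recurrent can be explained in ICG parameters" and will "evaluate the significance of the correlation coefficient using two sided t-test", with P below 0.05 called significant. It then turns to ROC curves: "Area under the ROC curve will be used to determine the optimal property".

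Section 7.2 takes a different route. For cohort 1, "SSI is the dependent variable and bone and tissue perfusion, as measured by ICG fluorescence, is the independent variable", and Tables 7.1 and 7.2 list the outcomes as binary. Variables are chosen by AUC and compared by Student's t-test. Then: "We will then apply multiple logistic model including ICG fluorescence and previously identified predictors for SSI". Cohort 2 follows the same pattern. Section 7.2 has no Pearson correlation or R-squared against infection; in section 7, R-squared appears only for DCE-MR against DCE-FI in cohort 2-1. For cohort 3, section 7.2 compares ICG between cohort categories and plans no infection analysis, although section 3.2 makes SSI that cohort's primary endpoint.

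**The concern.** There are two separate problems.

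The first is interpretation. When one variable is 0/1, r reflects both the separation between the groups and the share of patients who have the event. Two cohorts in which ICG discriminates equally well will give different R-squared values if their event rates differ. A reader told that R-squared is the variation in infection explained by ICG could take a low value as a weak marker. Relating perfusion to complications is a primary objective, so the summary of that relation matters.

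The second is validity of the test. Testing r against zero is algebraically the pooled-variance two-sample t-test. Section 7.1 assumes that the SD in the event group is twice that in the other group, and the event group is the smaller one. That is the arrangement in which the pooled test understates the standard error and rejects too often. Student's t-test in section 7.2 has the same weakness if, as is usual, it means the pooled version.

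**Working it through.** **Inputs, all from section 7.1.** Mean difference in I_max D = 24. SD 30 in the event group and 15 in the non-event group. Cohort 1: 10% events, 16 vs 144. Cohort 2: 30% events, 22 vs 52. Type I error 5%. Stated power 86% and 93%. No event rate is given for cohort 3; 2% to 5% is an assumption.

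**The plan's power figures.** For the two-sided Welch test, SE = √(SD1²/n1 + SD0²/n0).
- Cohort 1: √(900/16 + 225/144) = √57.81 = 7.60. Noncentrality 24/7.60 = 3.16, about 15.8 degrees of freedom, power 84.1% (stated 86%).
- Cohort 2: √(900/22 + 225/52) = √45.24 = 6.73. Noncentrality 24/6.73 = 3.57, about 25.6 degrees of freedom, power 92.9% (stated 93%).

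Both are within 2 points. The pooled-variance formula gives over 99% in each cohort and one-sided Welch gives 91.5% and 96.6%, so neither matches. SDs of 45 and 22.5 give 51% and 63%, so 30 and 15 already contain the 50% increase that section 7.1 mentions.

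**AUC.** For two normal groups, AUC = Φ(D/√(SD1² + SD0²)) = Φ(24/√1125) = Φ(0.716) = 0.763. The event rate does not enter.

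**R-squared.** With p the event proportion, R² = p(1−p)D² / [p(1−p)D² + p·SD1² + (1−p)·SD0²].

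| Event rate | p(1−p)·576 | p·900 + (1−p)·225 | R² |
|---|---|---|---|
| 10% (cohort 1) | 51.84 | 292.5 | 0.151 |
| 30% (cohort 2) | 120.96 | 427.5 | 0.221 |
| 2% (assumed, cohort 3) | 11.29 | 238.5 | 0.045 |
| 5% (assumed, cohort 3) | 27.36 | 258.75 | 0.096 |

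Separation moves R-squared too. At 10% events, SDs of 20 and 10 give 51.84/(51.84 + 130) = 0.285, with AUC 0.858.

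**Test of r.** t = r√(n−2)/√(1−r²) is identical to the pooled two-sample t. In simulated data the two P values agreed (2.66 × 10⁻⁶ from each in a 16 vs 144 sample).

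**Type I error of the pooled test, equal means, SDs 30 and 15.** Compare the standard error that the test uses with the true one.
- Cohort 1: pooled variance (15×900 + 143×225)/158 = 289.1. SE used √(289.1 × (1/16 + 1/144)) = 4.48; true SE 7.60; ratio 1.70. The critical value 1.975 acts like 1.975/1.70 = 1.16, a two-sided rejection rate of about 24%. Simulation gives about 25%.
- Cohort 2: pooled variance (21×900 + 51×225)/72 = 421.9. SE used √(421.9 × (1/22 + 1/52)) = 5.22; true SE 6.73; ratio 1.29. The critical value 1.993 acts like 1.993/1.29 = 1.55, about 12%. Simulation gives about 13%.

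The Welch test holds about 5% in both settings.

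**The case against.** The strongest defence is that R-squared is a side figure. The synopsis chooses the best parameter by AUC, and no threshold, power figure or primary test in section 7 uses R-squared for infection. It is also, literally, the variation explained by a linear fit to a 0/1 outcome. All of this stands, and it limits the interpretive problem to what a reader would make of the number.

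Several stronger readings are tempting but not supported:
- A reader might infer that R-squared is governed by the event rate. It depends on separation as well: going from 10% to 30% events moves it from 0.15 to 0.22, while the SD change shown above moves it from 0.15 to 0.285. At the planned sizes, 95% of simulated R-squared values lie in 0.03 to 0.34 (cohort 1) and 0.06 to 0.44 (cohort 2), so the 0.15 to 0.22 gap is within sampling noise.
- A reader might infer that the cohorts cannot be compared at all. Only R-squared has this defect. AUC is planned in the same paragraph, and the documents do not propose to compare R-squared between cohorts.
- A reader might infer a fixed ceiling on R-squared below 1. Under section 7.1's two-group inputs there is none; it tends to 1 as the difference grows.
- The low values for cohort 3 rest on an assumed event rate.

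The correlation is also not wholly redundant: it covers pre-debridement and change parameters, and it is the only infection analysis described for cohort 3 apart from the synopsis's ROC step. Removing it without a replacement would leave a gap.

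**Conclusion.** The point holds, at moderate weight. An R-squared against a yes/no outcome is not a measure of marker strength free of the event rate: the same marker (AUC 0.76) gives 0.15 at 10% events and 0.22 at 30%, and 0.05 to 0.10 at an assumed 2% to 5%. Taken alone, this would be mainly a matter of aligning the synopsis with section 7.2.

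The test is the weightier part. Under the plan's own SDs, the t-test of r has a two-sided type I error of about 25% (cohort 1) and 13% (cohort 2) against a nominal 5%, while the stated power corresponds to a test that the plan does not name. These rates assume normal data, equal true means, and the larger SD in the smaller group. Section 7.1 states that order for cohort 1, and it is taken to be the same for cohort 2. The rates depend on the SD ratio of 2 to 1, so the 50% increase applied to both SDs does not affect them. With equal SDs the inflation would vanish. Section 7.2 words its hypotheses in one direction, so the exact rates apply to the two-sided test in the synopsis.

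**What to change.** - In the synopsis, delete the Pearson correlation, the coefficient of determination and the t-test of r, and align the text with section 7.2.
- For each cohort, report the mean ICG difference between patients with and without the event with an unequal-variance (Welch) 95% CI, and the AUC with a 95% CI.
- In section 7.2 and Tables 7.1 and 7.2, name the unequal-variance t-test in place of Student's t-test. This also brings the analysis into line with the power statement in section 7.1.
- Add the same two estimates for cohort 3 to section 7.2 and label them descriptive. At the assumed 2% to 5%, 100 patients would yield 2 to 5 infections, so the intervals will be wide.

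The cost is small: wording in the synopsis and section 7.2, and one short added analysis for cohort 3. No further patients or data are needed. If the SDs prove equal, Welch gives up a little power relative to the pooled test, but the stated power already matches Welch.
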